#### **9.2.3.2 Pediatric Quality of Life Inventory Ages $> 2$ years**

The multidimensional PedsQL  $> 2$  years generic core scales encompass the following core domains for pediatric HRQoL measurement: Physical Functioning, Emotional Functioning, Social Functioning, and School Functioning.

Calculated values and changes from Baseline for the total scale score (all items), the psychosocial health summary score, the physical health summary score and each of the 4 scale scores will be summarized for each visit and for Last Visit. This will be repeated by enrollment group. For subjects 5 years and older at Baseline, changes from Baseline will be calculated for all visits, even when the questionnaire version used is different from the one at Baseline. For subjects less than 5 years at baseline, the change from Baseline will be calculated only when the same questionnaire version is used at Baseline and post-Baseline. All PedsQL  $> 2$  years data will be listed.

### **9.2.4 Health care resource use**

For health care resource use parameters, the following will be evaluated: concomitant medications (see Section 6.4), medical procedures, health care provider consultations not foreseen by the protocol, and hospitalization/ER visits. Health care resource use parameters will be collected according to the tabular schedules of study procedures.

#### **9.2.4.1 Healthcare provider consultations**

The number of healthcare provider consultations per subject for the Treatment Period will be summarized. The number of healthcare provider consultations will be summarized using the categories 0, 1, 2, 3, 4, and 5 or more.

The number of healthcare provider consultations during the Treatment Period will be summarized by type of provider (General Practitioner, Specialist Physician, Nurse, or Other). Percentages will be relative to the number of healthcare provider consultations during the Treatment Period.

All healthcare provider consultations data will be listed.

#### 9.2.4.2 Hospital stays and ER visits

The number of hospital stays per subject during the Treatment Period will be summarized. The number of hospital stays will be summarized using the categories 0, 1, 2, 3, 4, and 5 or more. The number and percentage of subjects with specific reasons for duration of hospital stays will be summarized for the duration of the Treatment Period.

The durations of hospital stays for the Treatment Period will be summarized. Duration of hospital stays (as defined in [Section 3.2.23](#)) will be categorized as 0 days, 1-5 days, 6-10 days, 11-15 days, and >15 days, and summarized for the duration of the Treatment Period.

An event logged on the Hospitalization/ER Visit eCRF module where ER is marked as initial entry point will be defined as an ER visit. An ER visit with a subject transfer to an inpatient general ward will also be counted as a hospitalization. However, all other instances of ER visits (where subject transfer is not to an inpatient general ward) will not be counted as hospitalizations. Descriptive statistics for the number of ER stays during the Treatment Period will be presented. The number of ER visits will be summarized using the categories 0, 1, 2, and 3 or more. The number and percentage of subjects with specific reasons for duration of ER visits will be summarized for the duration of the Treatment Period.

Hospitalizations with either a partial admission or discharge date are ignored for the calculation of duration of hospital stay. However, such hospitalizations are counted for the number of hospital stays. Subjects with no hospital stays will have a duration of 0 days. Should distinct records for hospital stays overlap, then the days during the overlap will only be counted once. Similarly this also applies for ER visits.

All hospitalization and ER data will be listed.

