4.2.3 Other efficacy variables

The following other efficacy variables will be computed for subjects from SP0969 and include the following:

- Percentage of 50% responders (subjects with at least a 50% reduction in total partial-onset seizure frequency per 28 days compared to Baseline), with Baseline defined as the period before receiving study medication in the previous pediatric study
- Percentage of 50% responders per seizure type (simple partial, complex partial, or secondarily generalized) compared with Baseline

- Percentage of 75% responders (subjects with at least a 75% reduction in total partial-onset seizure frequency per 28 days compared to Baseline), with Baseline defined as the period before receiving study medication in the previous pediatric study
- Percentage of 75% responders per seizure type (simple partial, complex partial, or secondarily generalized) compared with Baseline
- Absolute and percent reduction in total partial-onset seizures and per partial-onset seizure type (simple partial, complex partial, or secondarily generalized) compared to Baseline
- Partial-onset seizure frequency per 28 days

The following other efficacy variables will be computed for all subjects in EP0034 and include the following:

- Achievement of seizure-free status (no seizure) during the study for total partial-onset seizure and per seizure type (simple partial, complex partial, or secondarily generalized)
- Clinical Global Impression of Change
- Caregiver's Global Impression of Change
- Change from Baseline in PedsQL
- Health care resource use: concomitant medications, medical procedures, and health care provider consultations including hospitalizations not foreseen by the protocol

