10.2 Serious adverse events

10.2.1 Definition of serious adverse event

Once it is determined that a subject experienced an AE, the seriousness of the AE must be determined. An SAE must meet 1 or more of the following criteria:

- Death
- Life-threatening
(Life-threatening does not include a reaction that might have caused death had it occurred in a more severe form.)
- Significant or persistent disability/incapacity

- Congenital anomaly/birth defect (including that occurring in a fetus)
- Important medical event that, based upon appropriate medical judgment, may jeopardize the patient or subject and may require medical or surgical intervention to prevent 1 of the other outcomes listed in the definition of serious

(Important medical events may include but are not limited to, potential Hy's Law [see Section 10.3], allergic bronchospasm requiring intensive treatment in an emergency room or at home, blood dyscrasias that do not result in inpatient hospitalization, or the development of drug dependency or drug abuse.)

- Initial inpatient hospitalization or prolongation of hospitalization

(A patient admitted to a hospital, even if he/she is released on the same day, meets the criteria for the initial inpatient hospitalization. An emergency room visit that results in admission to the hospital would also qualify for the initial inpatient hospitalization criteria. However, emergency room visits that do not result in admission to the hospital would not qualify for this criteria and, instead, should be evaluated for 1 of the other criteria in the definition of serious [eg, life-threatening adverse experience, important medical event].

Hospitalizations for reasons not associated with the occurrence of an AE [eg, preplanned surgery or elective surgery for a pre-existing condition that has not worsened or manifested in an unusual or uncharacteristic manner] do not qualify for reporting. For example, if a subject has a condition recorded on his/her medical history and later has a preplanned surgery for this condition, it is not appropriate to record the surgery or hospitalization as an SAE, since there is no AE upon which to assess the serious criteria. Please note that, if the pre-existing condition has worsened or manifested in an unusual or uncharacteristic manner, this would then qualify as an AE and, if necessary, the seriousness of the event would need to be determined.)

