10.5 Anticipated serious adverse events

The following list of Anticipated SAEs has been identified, as these events are anticipated to occur in the population studied in this protocol at some frequency that is independent of drug exposure. This original list will remain in effect for the duration of the protocol.

This list does not change the investigator's obligation to report all SAEs (including Anticipated SAEs) as detailed in Section 10.2.2.

Table 10–1: Anticipated SAEs for the pediatric epilepsy population

MedDRA SOC	MedDRA PT
Congenital, familial and genetic disorders	Teratogenicity
General disorders and administration site conditions	Sudden unexplained death in epilepsy
Nervous system disorders	Convulsion
	Incontinence
	Status epilepticus
Pregnancy, puerperium and perinatal disorders	Abortion spontaneous
Psychiatric disorders	Psychotic behaviour
	Abnormal behaviour
	Anxiety
	Sleep disorder
Reproductive system and breast disorders	Menstrual disorder

MedDRA=Medical Dictionary for Regulatory Activities; PT=preferred term; SOC=system organ class; SAE=serious adverse event

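### SAP 9.2.4.2 counts an ER-entry admission as a hospital stay only on transfer to a general ward, so an ER admission to intensive care or a specialist unit with no later ward transfer is counted as no stay

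*SAP*

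**What the plan says.** Protocol 4.2.3 places health care resource use among the 'other' efficacy variables and includes "health care provider consultations including hospitalizations not foreseen by the protocol". Protocol 9.4 repeats this. Neither section restricts the type of ward. SAP 2.2.3.3 names hospital stays as a component of the same variable.

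SAP 9.2.4.2 then sets the counting rule in three steps:

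- Entry route: "An event logged on the Hospitalization/ER Visit eCRF module where ER is marked as initial entry point will be defined as an ER visit".
- Inclusion: "An ER visit with a subject transfer to an inpatient general ward will also be counted as a hospitalization".
- Exclusion: "However, all other instances of ER visits (where subject transfer is not to an inpatient general ward) will not be counted as hospitalizations".

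For durations, the same section says: "Subjects with no hospital stays will have a duration of 0 days". It also says: "All hospitalization and ER data will be listed".

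On seriousness of adverse events, protocol 10.2.1 says: "An emergency room visit that results in admission to the hospital would also qualify for the initial inpatient hospitalization criteria". No ward type is mentioned there.

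**The concern.** The third step leaves no room to read the general ward as a mere example of an inpatient destination. Nothing else in the SAP adds intensive care, a specialist unit or another hospital to the qualifying destinations. SAP 3.2.23 gives only the arithmetic for length of stay, and SAP 3.9 does not list the restriction as a change from the protocol.

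Three consequences follow. Some genuine inpatient stays are left out of the number and duration of hospital stays. Two identical stays in the same unit are counted or dropped according to whether the child came through the ER. And one admission can be serious by hospitalization in the adverse event tables yet not be a hospitalization in the resource-use tables.

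The case is a realistic one here. The protocol's list of anticipated serious adverse events (10.5) includes "Status epilepticus", an event that could plausibly come through the ER and need care outside a general ward.

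**Working it through.** The plan states no expected number of hospitalizations, so there is no figure to reproduce. The check applies the rule to each possible path and compares it with an admission-based rule in line with protocol 10.2.1.

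| Path | ER visits | Hospital stays, SAP as written | Hospital stays, any inpatient admission |
|---|---|---|---|
| ER, then home | 1 | 0 | 0 |
| ER, then general ward | 1 | 1 | 1 |
| ER, then intensive care or specialist unit, never a general ward | 1 | 0 | 1 |
| ER, then intensive care, then general ward | 1 | not settled by the text | 1 |
| Direct admission to intensive care | 0 | 1 (ward condition does not apply) | 1 |

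The third row is the fault. Set against the last row, it shows the dependence on entry route.

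**Duration for one stay.** SAP 3.2.23 gives duration = discharge date − admission date + 1. For illustration, a child enters through the ER on day 1, goes to intensive care and is discharged from there on day 7: 7 − 1 + 1 = 7 days. Under an admission-based rule this falls in the 6 to 10 day category. As written, if this is the child's only event, the child is in the 0 category for number of stays and the 0-day category for duration. If the child has another counted stay, the zero rule does not apply. The child's totals are then short by this one stay.

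**Share of stays lost.** Let p be the share of ER-route admissions that never reach a general ward. The number counted per 100 ER-route admissions is 100 × (1 − p). The documents give no value of p. Purely as an assumption:

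- p = 5%: 100 × 0.95 = 95 counted, 5 lost.
- p = 30%: 100 × 0.70 = 70 counted, 30 lost.
- Under an admission-based rule all 100 are counted.

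The base is ER-route admissions only. Direct admissions are not affected, so the share lost among all hospital stays is smaller. The share of ER-route hospital days lost equals p if these stays are as long as the others on average, and exceeds p if they are longer. The documents give no lengths of stay.

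**The case against.** The strongest objection is that the practical effect depends on a form the reader cannot see. The rule is tied to the Hospitalization/ER Visit eCRF module. If that form has no separate option for intensive care or a specialist unit, or uses the general ward option for any inpatient bed, little or nothing is lost. This stands as a limit on the size of the effect. It does not rescue the wording, because the SAP does not say so.

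Other parts of the objection also stand:

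- The SAP does not require the general-ward transfer to be the first one. A child who goes from the ER to intensive care and then to a ward may still qualify, with the whole stay counted from the ER date.
- A stay logged as its own record without ER entry is not touched by the exclusion.
- Protocol 10.2.1 defines hospitalization for seriousness, not for resource use, and the two measures need not match in every respect. Elective admissions, for instance, are treated there on their own terms. The difference supports an admission-based rule but is not by itself an error. The stronger grounds are the unequal treatment by entry route and the absence of any ward restriction in protocol 4.2.3 and 9.4.

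A reader might infer that severe seizure emergencies disappear from the study's results. They do not. They remain in the ER visit counts, the summary of ER reasons and the listings, and in the serious TEAE tables where they meet that definition.

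**Conclusion.** The rule as written gives a wrong count for one identifiable path: admission from the ER to an inpatient unit other than a general ward, with no later ward transfer. The bias in number and duration of stays can only be downward. Its size is unknown. The 5 to 30 per 100 ER-route admissions shown above is an assumption, not an estimate, and the loss could be close to nil if the eCRF uses the ward option broadly.

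A reader might go further and say that the rule removes the most severe and longest stays. The documents do not support that: the protocol's list of anticipated events says nothing about entry route, unit or length of stay. Nor does every intensive care stay drop out, given direct admissions and multi-step transfers.

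The consequence is limited. Health care resource use is a descriptive 'other' efficacy variable in a single-arm study with no hypothesis testing, and the primary safety variables are unaffected. The correction is still worth making, because it is cheap and the rule is stated rather than merely incomplete.

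**What to change.** In SAP 9.2.4.2, count an ER visit as a hospitalization whenever it results in inpatient admission to any unit: general ward, intensive care, specialist unit, or another hospital where inpatient admission is confirmed. The confirmation matters, since a transfer from one ER to another is not an admission. State that multi-step transfers qualify. Leave outside the count only ER visits without inpatient admission. List which transfer categories on the Hospitalization/ER Visit eCRF module map to each outcome. If the form cannot distinguish destinations, say so as a limitation of the hospital-stay summaries.

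The cost is a short SAP edit and one changed derivation condition. No new data should be needed if the form records the destination, which the documents do not allow one to confirm. The reported number and duration of stays may rise slightly.

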## 10 PHARMACOKINETICS AND PHARMACODYNAMICS

This section is not applicable for this study.

## 11 REFERENCES

This section is not applicable for this study.

**PUBLIC COPY**  
This document cannot be used to support any marketing authorization application and any extensions or variations thereof.

## 12 APPENDICES

### 12.1 Marked abnormality criteria for laboratory data

#### 12.1.1 Marked abnormality criteria for hematology data

Table 12–1: Hematology abnormality criteria

Parameter	Age Range	Unit (conventional)	Abnormality criteria (conventional unit)	Unit (standard)	Abnormality criteria (standard unit)
Hematocrit	<2y	%	≤27 >45	%	≤27 >45
	2y - <17y	%	≤29 >47	%	≤29 >47
	≥17y	%	≤85% of LLN >115% of ULN	%	≤85% of LLN >115% of ULN
Hemoglobin	<2y	g/dL	≤9.0	g/L	≤90
	2y - <17y	g/dL	≤9.5	g/L	≤95
	≥17y	g/dL	≤85% of LLN	g/L	≤85% of LLN
WBC/ Leukocytes	All	10  /L	≤3.0 >16.0	G/L	≤3.0 >16.0
Lymphocytes Absolute	<2y	10  /L	<1.0 >8.0	G/L	<1.0 >8.0
	2y - <6y	10  /L	<0.7 >6.9	G/L	<0.7 >6.9
	≥6y	10  /L	<0.6 >5.0	G/L	<0.6 >5.0
Basophils	>1m	%	≥5.0	%	≥5.0
Basophils Absolute	>1m	10  /L	≥0.4	G/L	≥0.4
Eosinophils	>1m	%	≥10	%	≥10
Eosinophils Absolute	>1m	10  /L	≥1.0	G/L	≥1.0
Monocytes	>1m	%	≥20.0	%	≥20.0

**Table 12–1: Hematology abnormality criteria**

Parameter	Age Range	Unit (conventional)	Abnormality criteria (conventional unit)	Unit (standard)	Abnormality criteria (standard unit)
Monocytes Absolute	>1m	10  /L	≥2.0	G/L	≥2.0
Neutrophils Absolute	>1m	10  /L	<1.5	G/L	<1.5
Platelets	>1m	10  /L	≤100 >600	G/L	≤100 ≥600
RBC/ Erythrocytes	<2y ≥2y	10  /L	<3.0 <3.5	T/L T/L	<3.0 <3.5

Abbreviations: ANC=absolute neutrophil count; m=months, y= years. A month is defined as 28 days; a year is defined as 365.25 days.

This document cannot be used to support any marketing authorization application and any extensions or variations thereof.

**12.1.2 Marked abnormality criteria for chemistry data**

**Table 12–2: Chemistry abnormality criteria**

Parameter	Age Range	Unit (conventional)	Abnormality criteria (conventional unit)	Unit (standard)	Abnormality criteria (standard unit)
AST (SGOT)	All	U/L	≥3.0 x ULN ≥5.0 x ULN	U/L	≥3.0 x ULN ≥5.0 x ULN
ALT (SGPT)	All	U/L	≥3.0 x ULN ≥5.0 x ULN	U/L	≥3.0 x ULN ≥5.0 x ULN
Alkaline Phosphatase	<4y	U/L	≥690	U/L	≥690
	4y - <10y	U/L	≥834	U/L	≥834
	10y - <17y	U/L	≥1761	U/L	≥1761
	≥17y	U/L	≥3.0 x ULN	U/L	≥3.0 x ULN
GGT	<6m	U/L	≥522	U/L	≥522
	6m - <1y	U/L	≥279	U/L	≥279
	1y - <13y	U/L	≥66	U/L	≥66
	13y - <17y	U/L	≥126	U/L	≥126
	≥17y	U/L	≥3.0 x ULN	U/L	≥3.0 x ULN
Total Bilirubin	>1m	mg/dL	≥2.0	umol/L	≥34.208
Total Protein	2m-<1y	g/dL	<3.0 >11.9	g/L	<30 >119
	1y - <17y	g/dL	<4.3 >12.0	g/L	<43 >120
	≥17y	g/dL	<4.3 >13.0	g/L	<43 >130
	Albumin	<1y	g/dL	<1.6 >7.2	g/L
Albumin	≥1y - <17y	g/dL	<2.4 >8.4	g/L	<24 >84
	≥17y	g/dL	<2.6 >8.4	g/L	<26 >84
BUN	<1y	mg/dL	≥24	mmol/L	≥8.568
	1y - <17y	mg/dL	≥36	mmol/L	≥12.852

Parameter	Age Range	Unit (conventional)	Abnormality criteria (conventional unit)	Unit (standard)	Abnormality criteria (standard unit)
	≥17y	mg/dL	≥40	mmol/L	≥14.28
Urea	<1y	mg/dL	>42	mmol/L	>7.014
	≥1y	mg/dL	>60	mmol/L	>10.02
Creatinine	1y - <10y	mg/dL	>1.2	umol/L	>106.8
	10y - <16y	mg/dL	>1.8	umol/L	>159.12
	≥16y	mg/dL	≥2.0	umol/L	≥176.8
Creatinine Clearance a,b	All	mL/min	<50	mL/s	<0.835
Bicarbonate	>1m - <17y	mEq/L	<15 >38	mmol/L	<15 >38
	≥17y	mEq/L	<18 >38	mmol/L	<18 >38
Calcium	<1y	mg/dL	<6.9 >12.2	mmol/L	<1.725 >3.05
	1y - <17y	mg/dL	<7.4 >11.7	mmol/L	<1.85 >2.925
	≥17y	mg/dL	≤7.6 ≥11.0	mmol/L	≤1.9 ≥2.75
Chloride	>1m	mEq/L	≤90 ≥112	mmol/L	≤90 ≥112
Phosphorous	<1y	mg/dL	<1.8 >8.2	mmol/L	<0.5814 >2.6486
	1y - <17y	mg/dL	<1.8 >7.4	mmol/L	<0.5814 >2.3902
	≥17y	mg/dL	≤2.0 ≥6.0	mmol/L	≤0.646 ≥1.938
Potassium	<1y	mEq/L	≤3.0 ≥6.5	mmol/L	≤3.0 ≥6.5
	≥1y	mEq/L	≤3.0 ≥6.0	mmol/L	≤3.0 ≥6.0

Parameter	Age Range	Unit (conventional)	Abnormality criteria (conventional unit)	Unit (standard)	Abnormality criteria (standard unit)
Sodium	>1m	mEq/L	<127 >151	mmol/L	<127 >151
Glucose	>1m - <17y	mg/dL	<50 ≥180	mmol/L	<2.775 ≥9.99
	≥17y	mg/dL	<50 ≥200	mmol/L	<2.775 ≥11.1
Total Cholesterol	≥1y	mg/dL	>250	mmol/L	>6.475
LDL (calculated)	1y - <17y	mg/dL	>140	mmol/L	>3.626
	≥17y	mg/dL	>200	mmol/L	>5.18
HDL	≤2y	mg/dL	<10	mmol/L	<0.259
	>2y	mg/dL	<20	mmol/L	<0.518
Triglycerides	<1y	mg/dL	>750	mmol/L	>8.475
	≥1y	mg/dL	>300	mmol/L	>3.39
Uric Acid	<1y	mg/dL	>7.7	umol/L	>457.996
	1y - <13y	mg/dL	>6.5	umol/L	>386.62
	13y - <17y	mg/dL	>8.6	umol/L	>511.528
	≥17y	mg/dL	>9.5	umol/L	>565.06
Thyroxine (T4)	<1y	ug/dL	≤4.3 ≥18.4	nmol/L	≤55.3453 ≥236.8264
	≥1y	ug/dL	≤3.8 ≥13.5	nmol/L	≤48.9098 ≥173.7585
Globulin	<1y	g/dL	<1.0 >4.5	g/L	<10 >45
	≥1y	g/dL	<1.2 >5.3	g/L	<12 >53

Abbreviations: ALT=alanine aminotransferase; AST=aspartate aminotransferase; BUN=blood urea nitrogen; dL=deciliter; GGT=gamma-glutamyl transferase; HDL=high density lipoprotein; LDL=low density lipoprotein; L=liter; m=months (a month is defined as 28 days) mg=milligram; mmol=millimoles; µg=microgram; U=unit; ULN=upper limit of normal; y=years (a year is defined as 365.25 days)

a Schwartz equation (subjects <12): Cr Cl ml/min=[Height (cm) \* 0.55] / serum creatinine

b Cockcroft equation (subjects >12): Male: Cr Cl ml/min=[(140-age) x body weight (kg)] / (72 x serum creatinine); Female: Cr Cl ml/min=[(140-age) x body weight (kg)] / (72 x serum creatinine) x 0.85

## 12.2 Other Significant AEs

The following MedDRA PTs are defined as other significant TEAEs.

**Table 12–3: Other significant TEAEs**

MedDRA Preferred Term
CARDIAC AND ECG RELATED TERMS
Atrial conduction time prolongation
Atrial fibrillation
Atrial flutter
Atrioventricular block second degree
Atrioventricular block third degree
Atrioventricular dissociation
Bradyarrhythmia
Bradycardia
Brugada syndrome
Cardiac arrest
Cardiac fibrillation
Cardiac flutter
Cardiac pacemaker insertion
Conduction disorder
Defect conduction intraventricular
Electrocardiogram QT prolonged
Heart Rate decreased
Implantable defibrillator insertion

**Table 12–3: Other significant TEAEs**

MedDRA Preferred Term
Sick sinus syndrome
Sinus arrest
Sinus bradycardia
Torsade de pointes
Ventricular asystole
Ventricular fibrillation
Ventricular flutter
Ventricular tachyarrhythmia
Ventricular tachycardia
SUICIDALITY RELATED TERMS
Completed suicide
Depression suicidal
Intentional overdose
Intentional self-injury
Multiple drug overdose intentional
Poisoning deliberate
Self injurious behaviour
Self-injurious ideation
Suicidal behaviour
Suicidal ideation
Suicide attempt
ADDITIONAL TERMS
Abnormal behaviour

**Table 12–3: Other significant TEAEs**

MedDRA Preferred Term
Appetite disorder
Decreased appetite
Diet refusal
Food aversion
Hypophagia
Loss of consciousness
Syncope

**12.3 List of AEs for Potentially Drug Induced Liver Injury (PDILI)**

The following MedDRA PTs are defined as AEs for Potentially Drug Induced Liver Injury:

**Table 12–4: AEs for PDILI**

MedDRA Preferred Term for PDILI
Acute hepatic failure
Alanine aminotransferase increased
Allergic hepatitis
Aspartate aminotransferase increased
Asterixis
Blood bilirubin abnormal
Blood bilirubin increased
Cholestasis
Cholestatic liver injury
Cholestatic pruritus

Chronic hepatitis
Coma hepatic
Cryptogenic cirrhosis
Drug-induced liver injury
Hepatic cirrhosis
Hepatic encephalopathy
Hepatic failure
Hepatic infiltration eosinophilic
Hepatic necrosis
Hepatic steatosis
Hepatitis
Hepatitis acute
Hepatitis cholestatic
Hepatitis chronic active
Hepatitis chronic persistent
Hepatitis fulminant
Hepatitis toxic
Hepatobiliary disease
Hepatocellular foamy cell syndrome
Hepatocellular injury
Hepatotoxicity
Hyperbilirubinaemia
Icterus index increased
Jaundice
Jaundice cholestatic

Jaundice hepatocellular
Liver disorder
Liver injury
Mixed liver injury
Non-alcoholic steatohepatitis
Ocular icterus
Subacute hepatic failure

PUBLIC COPY  
This document cannot be used to support any marketing authorization application and any extensions or variations thereof.

